4.4.5 Treatment Beyond Disease Progression

Accumulating evidence indicates a minority of subjects treated with immunotherapy may derive clinical benefit despite initial evidence of Progressive Disease (PD).

Subjects will be permitted to continue treatment beyond initial RECIST 1.1 defined PD, up to a maximum of 2 years treatment, as long as they meet the following criteria:

- Investigator-assessed clinical benefit, and
- Subject is tolerating study drug.
- Stable performance status

- Treatment beyond progression will not delay an imminent intervention to prevent serious complications of disease progression (eg, CNS metastases)
- Subject provides written informed consent prior to receiving additional study medication, All other elements of the main informed consent including the description of reasonably foreseeable risks or discomforts, or other alternative treatment options will still apply.

A radiographic assessment/scan should be performed within 6 weeks of initial investigator-assessed progression to determine whether there has been a decrease in the tumor size or continued PD. The assessment of clinical benefit should be balanced by clinical judgment as to whether the subject is clinically deteriorating and unlikely to receive any benefit from continued treatment with nivolumab.

If the investigator feels that the subject continues to achieve clinical benefit by continuing treatment, the subject should remain on the trial and continue to receive monitoring according to the Time and Events Schedule on [Section 5](#).

For the subjects who continue study therapy beyond progression, further progression is defined as an additional 10% increase in tumor burden with a minimum of 5 mm absolute increase from time of initial PD. This includes an increase in the sum of diameters of all target lesions and/ or the diameters of new measurable lesions compared to the time of initial PD. Treatment with study medication should be discontinued permanently upon documentation of further progression.

New lesions are considered measureable at the time of initial progression if the longest diameter is at least 10 mm (except for pathological lymph nodes which must have a short axis of at least 15 mm). Any new lesion considered non-measureable at the time of initial progression may become measureable and therefore included in the tumor burden if the longest diameter increases to at least 10 mm (except for pathological lymph nodes which must have a short axis of at least 15 mm). In situations where the relative increase in total tumor burden by 10% is solely due to inclusion of new lesions which become measurable, these new lesions must demonstrate an absolute increase of at least 5 mm.

4.4.6 Management Algorithms for Immuno-Oncology Agents

Immuno-oncology (I-O) agents are associated with AEs that can differ in severity and duration than AEs caused by other therapeutic classes. Nivolumab and ipilimumab are considered I-O agents in this protocol. Early recognition and management of AEs associated with I-O agents may mitigate severe toxicity. Management Algorithms have been developed to assist investigators in assessing and managing the following groups of AEs:

- Gastrointestinal
- Renal
- Pulmonary
- Hepatic
- Endocrinopathy

- Skin
- Neurological.

The above algorithms are found in [Appendix 3](#).

4.4.7 Treatment of Nivolumab or Ipilimumab Related Infusion Reactions

Since nivolumab and ipilimumab contains only human immunoglobulin protein sequences, it is unlikely to be immunogenic and induce infusion or hypersensitivity reactions. However, if such a reaction were to occur, it might manifest with fever, chills, rigors, headache, rash, pruritus, arthralgias, hypotension, hypertension, bronchospasm, or other allergic-like reactions. All Grade 3 or 4 infusion reactions should be reported within 24 hours to the study medical monitor and reported as an SAE if it meets the criteria. Infusion reactions should be graded according to NCI CTCAE (Version 4.0) guidelines.

Treatment recommendations are provided below and may be modified based on local treatment standards and guidelines, as appropriate:

For Grade 1 symptoms (mild reaction; infusion interruption not indicated; intervention not indicated):

- Remain at bedside and monitor subject until recovery from symptoms. The following prophylactic premedications are recommended for future infusions: diphenhydramine 50 mg (or equivalent) and/or acetaminophen/paracetamol 325 to 1000 mg at least 30 minutes before additional nivolumab administrations.

For Grade 2 symptoms: (moderate reaction required therapy or infusion interruption but responds promptly to symptomatic treatment (eg, antihistamines, non-steroidal antiinflammatory drugs, narcotics, corticosteroids, bronchodilators, IV fluids); prophylactic medications indicated for ≤ 24 hours):

- Stop the study drug infusion, begin an IV infusion of normal saline, and treat the subject with diphenhydramine 50 mg IV (or equivalent) and/or acetaminophen/paracetamol 325 to 1000 mg; remain at bedside and monitor subject until resolution of symptoms. Corticosteroid and/or bronchodilator therapy may also be administered as appropriate. If the infusion is interrupted, then restart the infusion at 50% of the original infusion rate when symptoms resolve; if no further complications ensue after 30 minutes, the rate may be increased to 100% of the original infusion rate. Monitor subject closely. If symptoms recur, then no further study medication will be administered at that visit.
- For future infusions, the following prophylactic premedications are recommended: diphenhydramine 50 mg (or equivalent) and/or acetaminophen/paracetamol 325 to 1000 mg should be administered at least 30 minutes before nivolumab and/or ipilimumab infusions. If necessary, corticosteroids (up to 25 mg of hydrocortisone or equivalent) may be used.

For Grade 3 or 4 symptoms: (severe reaction, Grade 3: prolonged [ie, not rapidly responsive to symptomatic medication and/or brief interruption of infusion]; recurrence of symptoms following initial improvement; hospitalization indicated for other clinical sequelae (eg, renal impairment, pulmonary infiltrates). Grade 4: Life threatening; pressor or ventilatory support indicated):

- Immediately discontinue infusion of study drug. Begin an IV infusion of normal saline and treat the subject as follows: Recommend bronchodilators, epinephrine 0.2 to 1 mg of a 1:1000 solution for subcutaneous administration or 0.1 to 0.25 mg of a 1:10,000 solution injected slowly for IV administration, and/or diphenhydramine 50 mg IV with methylprednisolone 100 mg IV (or equivalent), as needed. Subject should be monitored until the Investigator is comfortable that the symptoms will not recur. Study drug will be permanently discontinued. Investigators should follow their institutional guidelines for the treatment of anaphylaxis. Remain at bedside and monitor subject until recovery of the symptoms.

In case of late-occurring hypersensitivity symptoms (eg, appearance of a localized or generalized pruritus within 1 week after treatment), symptomatic treatment may be given (eg, oral antihistamine or corticosteroids).

4.5 Selection and Timing of Dose for Each Subject

The dosing regimen and schedule for Parts 1 and 2 are detailed in Table 4.5-1 and Table 4.5-2, respectively.

Note: The first flat dose 480 mg nivolumab in Part 2 will be administered 6 weeks after the last combination dose in Part 1.

Table 4.5-1: Dosing Schedule for Part 1 (Double-Blinded)				
Every 3 weeks dosing 1 cycle = 3 weeks				
	Cycle 1	Cycle 2	Cycle 3	Cycle 4
Arm A	Nivolumab 3 mg/kg Ipilimumab 1 mg/kg	Nivolumab 3 mg/kg Ipilimumab 1 mg/kg	Nivolumab 3 mg/kg Ipilimumab 1 mg/kg	Nivolumab 3 mg/kg Ipilimumab 1 mg/kg
Arm B	Nivolumab 1 mg/kg Ipilimumab 3 mg/kg	Nivolumab 1 mg/kg Ipilimumab 3 mg/kg	Nivolumab 1 mg/kg Ipilimumab 3 mg/kg	Nivolumab 1 mg/kg Ipilimumab 3 mg/kg

Table 4.5-2: Dosing Schedule for Part 2 (Open Label)	
Every 4 weeks dosing 1 cycle = 4 weeks, Cycle 5 to begin 6 weeks after Cycle 4 ^a	
	Cycle 5 and beyond
Arms A and B	Flat dose 480 mg nivolumab

^a Cycle X - Cycle 8, 9, etc until disease progression or unacceptable toxicity or a maximum treatment of 2 years.

4.6 Blinding/Unblinding

The sponsor, subjects, investigator, and site staff will be blinded to the study drug administered during Part 1 (Combination Portion) of the study. Each investigative site must assign an unblinded pharmacist/designee, and an unblinded site monitor will be assigned by sponsor to provide oversight of drug supply and other unblinded study documentation.

During Part 2 (monotherapy portion), 480 mg nivolumab administered as a flat dose will be open-label. However, subject's treatment assigned arm during Part 1 must not be revealed until end of study.

Blinding of treatment assignment is critical to the integrity of this clinical study. Hence, every effort should be made to maintain the blind. However, in the event of a medical emergency or pregnancy in an individual subject in which knowledge of the investigational product is critical to the subject's management, the blind for that subject may be broken by the investigator. The subject's safety takes priority over any other considerations in determining if a treatment assignment should be unblinded.

Before breaking the blind of an individual subject's treatment, the investigator should determine that the unblinded information is necessary, ie, that it will alter the subject's immediate management. In many cases, particularly when the emergency is clearly not related to the investigational product, the problem may be properly managed by assuming that the subject is receiving active product. It is highly desirable that the decision to unblind treatment assignment be discussed with the Medical Monitor, but the investigator always has ultimate authority for the decision to unblind. The Principal Investigator should only call in for emergency unblinding AFTER the decision to discontinue the subject has been made.

- For this study, the method of unblinding for emergency purposes is through IRT. For information on how to unblind form emergency, please consult the IRT manual.
- In cases of accidental unblinding, contact the Medical Monitor and ensure every attempt is made to preserve the blind.
- Any request to unblind a subject for non-emergency purposes should be discussed with the Medical Monitor.

Designated staff of Bristol-Myers Squibb Research & Development may be unblinded prior to database lock to facilitate the bioanalytical analysis of pharmacokinetic samples and immunogenicity. A bioanalytical scientist in the Bioanalytical Sciences department of Bristol-Myers Squibb Research & Development (or a designee in the external central bioanalytical laboratory) will be unblinded to the randomized treatment assignments in order to minimize unnecessary bioanalytical analysis of samples.

4.7 Treatment Compliance

Treatment compliance will be monitored by drug accountability as well as the subject's medical record and electronic case report form (eCRF).

4.8 Destruction of Study Drug

For this study, study drugs (those supplied by BMS or sourced by the investigator) such as partially used study drug containers, vials and syringes may be destroyed on site.

Any unused study drugs can only be destroyed after being inspected and reconciled by the responsible Study Monitor unless study drug containers must be immediately destroyed as required for safety, or to meet local regulations (eg, cytotoxics or biologics).

On-site destruction is allowed provided the following minimal standards are met:

- On-site disposal practices must not expose humans to risks from the drug.
- On-site disposal practices and procedures are in agreement with applicable laws and regulations, including any special requirements for controlled or hazardous substances.
- Written procedures for on-site disposal are available and followed. The procedures must be filed with the site's SOPs and a copy provided to BMS upon request.
- Records are maintained that allow for traceability of each container, including the date disposed of, quantity disposed, and identification of the person disposing the containers. The method of disposal, ie, incinerator, licensed sanitary landfill, or licensed waste disposal vendor must be documented.
- Accountability and disposal records are complete, up-to-date, and available for the Monitor to review throughout the clinical trial period.

If conditions for destruction cannot be met the responsible Study Monitor will make arrangements for return of study drug.

It is the investigator's responsibility to arrange for disposal of all empty containers, provided that procedures for proper disposal have been established according to applicable federal, state, local, and institutional guidelines and procedures, and provided that appropriate records of disposal are kept.

4.9 Return of Study Drug

If study drug will not be destroyed upon completion or termination of the study, all unused and/or partially used study drug that was supplied by BMS must be returned to BMS. The return of study drug will be arranged by the responsible Study Monitor.

It is the investigator's responsibility to arrange for disposal of all empty containers, provided that procedures for proper disposal have been established according to applicable federal, state, local, and institutional guidelines and procedures, and provided that appropriate records of disposal are kept.

4.10 Retained Samples for Bioavailability / Bioequivalence

Not Applicable.

5 STUDY ASSESSMENTS AND PROCEDURES

5.1 Flow Chart/Time and Events Schedule

Table 5.1-1: Screening Assessments (CA209511)		
Procedure	Screening Visit	Notes
Eligibility Assessments		
Informed Consent	X	Prior to any screening procedures.
Inclusion/Exclusion Criteria	X	All inclusion/exclusion criteria should be assessed at screening and confirmed prior to randomization.
Medical History	X	
Tumor Tissue Samples	X	Sufficient tumor tissue obtained in the metastatic setting or from an unresectable site (block or minimum of 10 slides, obtained from core biopsy, punch biopsy, excisional biopsy or surgical specimen) In order to be randomized, a subject must be have quantifiable PD-L1 expression ($\geq 5\%$ or $< 5\%$ tumor cell membrane staining) or be classified as PD-L1 indeterminate.
Safety Assessments		
Physical Examination	X	Including pulmonary assessment
Vital Signs	X	Including BP, HR, temperature. Obtain vital signs at the screening visit and within 72 hours prior to first dose. (Section 5.3)
Physical Measurements (including performance status)	X	Height, Weight and ECOG Performance status
Assessment of Signs and Symptoms	X	Within 14 days prior to first dose
Concomitant Medication Collection	X	Within 14 days prior to first dose
Laboratory Tests	X	CBC w/differential, Chemistry panel including: Albumin, LDH, AST, ALT, ALP, T.Bili, BUN or serum urea level, creatinine, Ca, Mg, Na, K, Cl, Glucose, amylase, lipase, TSH, Free T4, Free T3, hepatitis B surface antigen (HBV sAg), and hepatitis C antibody (HCV Ab) or Hepatitis C RNA (HCV RNA), within 14 days prior to randomization

Table 5.1-1: Screening Assessments (CA209511)		
Procedure	Screening Visit	Notes
Pregnancy Test (WOCBP only)	X	
Screening/Baseline Tumor Assessment	X	Chest, Abdomen, Pelvis, and Brain within 28 days prior to first dose. Head MRI is required in subjects with known history of brain metastases; subjects without known history of brain metastases may have head CT or MRI.

Table 5.1-2: On-Study Assessments Part 1 (CA209511)		
Procedure	For Part 1, Study Drug Every 3 Weeks for 4 Cycles (Both Arm A and Arm B)	Notes
	Cycle 1, 2, 3, 4 (Day 1)	
Safety Assessments		
Targeted Physical Examination	X	To be performed only as clinically indicated within 72 hours prior to dosing
Vital Signs	X	Including BP, HR, temperature. (Section 5.3)
Physical Measurements (including performance status)	X	Weight and ECOG Performance status within 72 hours prior to dosing
Adverse Events Assessment	Continuously	
Review of Concomitant Medications	X	
Laboratory Tests	X	Within 72 hrs prior to dosing to include CBC w/ differential, LFTs, BUN or serum urea level, creatinine, Ca, Mg, Na, K, Cl, LDH, Glucose, amylase, lipase, TSH (+ reflex Free T4 and Free T3), albumin if clinically indicated).
Pregnancy Test (WOCBP only)	X	Serum or urine within 24 hours prior to administration of first dose and every 3 weeks thereafter in Part 1 of the study.
Pharmacokinetic and Immunogenicity Assessments		
Immunogenicity blood sample	See Section 5.5 for details regarding specific sample timing	
PK Samples	See Section 5.5 for details regarding specific sample timing	

Table 5.1-2: On-Study Assessments Part 1 (CA209511)		
Procedure	For Part 1, Study Drug Every 3 Weeks for 4 Cycles (Both Arm A and Arm B)	Notes
	Cycle 1, 2, 3, 4 (Day 1)	
Exploratory Biomarker Testing		
Exploratory Serum Biomarkers	X	To be collected pre-dose; before first 4 combination doses only.
Peripheral Blood Mononuclear Cells (PBMCs)	X	To be collected pre-dose; before first 4 combination doses only. To be collected in USA and Canada only.
Whole Blood Sample (DNA)	X	X = before first combination dose only.
Myeloid-Derived Suppressor Cell (MDSCs)	X	To be collected pre-dose; before the first and the third combination dose only
Efficacy Assessment		
Tumor Assessment	See Notes	FIRST tumor assessment should be performed at 12 weeks (\pm 1 wk) following randomization. CT Chest, CT (or MRI) abdomen, pelvis and all known sites of disease. Use same imaging method as was used at screening/baseline. Subjects with a history of brain metastasis should have surveillance MRI approximately every 12 weeks, or sooner if clinically indicated

Table 5.1-2: On-Study Assessments Part 1 (CA209511)		
Procedure	For Part 1, Study Drug Every 3 Weeks for 4 Cycles (Both Arm A and Arm B)	Notes
	Cycle 1, 2, 3, 4 (Day 1)	
Outcomes Research Assessments		
EORTC QLQ-C30 and EQ-5D	X	To be completed at the start of the clinic visit every 6 weeks. First questionnaire should be completed after IRT randomization but before dosing. (Cycle 1, 3)
Health Care Utilization	X	Health Care Utilization will be collected at each visit
Clinical Drug Supplies		
IRT Drug Vial Assignment	X	Within 24 hours prior to dosing
Administer Study Treatment	X	First dose to be administered within 3 days following randomization. See Section 4.3 .

Table 5.1-3: On-Study Assessments - Part 2 (CA209511)		
Procedure	For Part 2, Study Drug is Administered Every 4 Weeks (Both Arm A and Arm B)	Notes Cycle 5 will begin 6 weeks after Cycle 4
	Cycle 5 and beyond (Day 1)	
Safety Assessments		
Targeted Physical Examination	X	To be performed only if clinically indicated within 72 hours prior to dosing
Vital Signs	X	Including BP, HR, temperature (Section 5.3)
Physical Measurements (including performance status)	X	Weight and ECOG Performance status within 72 hours prior to dosing
Adverse Events Assessment	Continuously	
Review of Concomitant Medications	X	
Laboratory Tests	X	Beginning at Cycle 5 and every alternate dose thereafter (Cycle 7, 9, 11, 13, etc), on-study local laboratory assessments should be done within 72 hours prior to the first (Part 2) dose and include: CBC w/differential, LFTs (ALT, AST, total bilirubin, alkaline phosphatase), BUN or serum urea level, creatinine, Ca, Mg, Na, K, Cl, LDH, glucose, amylase, lipase, TSH with reflexive Free T4, Free T3. (Albumin if clinically indicated) Beginning at Cycle 6 and every alternate dose thereafter (Cycle 8, 10, 12, 14, etc), on-study local laboratory assessment should be done within 72 hours prior to the second (Part 2) dose and include: LFTs (ALT, AST, total bilirubin, alkaline phosphatase) and creatinine.
Pregnancy Test (WOCBP only)	X	Serum or urine within 24 hours prior to first dose and every 4 weeks thereafter in Part 2

Table 5.1-3: On-Study Assessments - Part 2 (CA209511)		
Procedure	For Part 2, Study Drug is Administered Every 4 Weeks (Both Arm A and Arm B)	Notes Cycle 5 will begin 6 weeks after Cycle 4
	Cycle 5 and beyond (Day 1)	
Outcomes Research Assessments		
EORTC QLQ-C30 and EQ-5D	X	To be completed at the start of the clinic visit every 4 weeks from Cycles 5 to 11
Health Care Utilization		Health Care Utilization will be collected at each visit
Pharmacokinetic and Immunogenicity Assessments		
Immunogenicity blood sample	See Section 5.5 for details regarding specific sample timing	
PK Samples	See Section 5.5 for details regarding specific sample timing	
Efficacy Assessment		
Tumor Assessment	See Notes	
First tumor assessment during Part 2 should occur after 8 weeks (\pm 1wk) relative to previous tumor assessment performed at week 12.
 
Subsequent tumor assessments should occur every 8 weeks (\pm 1 wk) for the first 12 months from randomization.
 
From the second year from randomization, tumor assessments should occur every 12 wks (\pm 2 wk) until disease progression.
 
CT Chest, CT (or MRI) abdomen, pelvis and all known sites of disease. Use same imaging method as was used at screening/baseline.
 
Subjects with a history of brain metastasis should have surveillance MRI approximately every 12 weeks, or sooner if clinically indicated.

Table 5.1-3: On-Study Assessments - Part 2 (CA209511)		
Procedure	For Part 2, Study Drug is Administered Every 4 Weeks (Both Arm A and Arm B)	Notes Cycle 5 will begin 6 weeks after Cycle 4
	Cycle 5 and beyond (Day 1)	
Clinical Drug Supplies		
IRT Drug Vial Assignment	X	
Administer Study Treatment	X	See Section 4.3 . Note: Within 3 days from vial assignment, the subject must receive the dose of study medication.

Table 5.1-4: Follow-up Assessments (CA209511)			
Procedure	Follow Up,^a Visits X1 and X2	Survival,^b Follow-up Y Visits	Notes
Safety Assessments			
Targeted Physical Examination	X		To assess for potential late emergent study drug related issues
Adverse Event Assessments	X	X	
Laboratory Tests	X		On site/local CBC w/differential, LFTs, BUN, creatinine, amylase, lipase and TSH (+ reflex Free T4 and Free T3) for X1, repeat at X2 if study drug related toxicity persists.
Pregnancy Test (WOCBP Only)	X		Serum or urine
Review of Concomitant Medications	X		
Pharmacokinetic Samples and Immunogenicity Assessments			
PK Samples	X		See Section 5.5 for schedule of assessments
Immunogenicity blood sample	X		Refer to Section 5.5 for details regarding specific sample timing
Survival Status			
Subject Status	X	X	Every 3 months, Survival Follow up Visits may be accomplished by visit or phone contact, to include subsequent anti-cancer therapy

Table 5.1-4: Follow-up Assessments (CA209511)			
Procedure	Follow Up,^a Visits X1 and X2	Survival,^b Follow-up Y Visits	Notes
Efficacy Assessments			
Tumor Assessments	See Notes		
Only for subjects without progression on study therapy.
 
FIRST tumor assessment should first be performed at 12 weeks (± 1 wk) following randomization
 
SUBSEQUENT tumor assessments should occur every 8 weeks (± 1 wk) thereafter for the first 12 months, then every 12 wks (± 2 wk) until disease progression
 
CT Chest, CT (or MRI) abdomen, pelvis and all known sites of disease. Use same imaging method as was used at screening/baseline.
 
Subjects with a history of brain metastasis should have surveillance MRI approximately every 12 weeks, or sooner if clinically indicated

Exploratory Biomarker Testing			
Tumor Tissue Biopsy	X	X	Optional; collection upon progression

^a X visits occur as follows - X1 = 30 days from the last dose (± 7 days) or coincide with the date of discontinuation (± 7 days) if date of discontinuation is greater than 37 days after last dose, X2 = 84 days (± 7 days) from follow-up visit 1. Follow up visits X1 and X2 will occur only after patient completes all study treatment.

^b Y Survival visits = every 3 months from X2 (± 7 days).

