- Active brain metastases or leptomeningeal metastases. Subjects with brain metastases are eligible if these have been treated and there is no evidence of progression via magnetic resonance imaging (MRI, except where contraindicated in which CT scan is acceptable) for at least 8 weeks after treatment is complete and within 28 days prior to first dose of study drug administration. There must also be no requirement for high doses of systemic corticosteroids that could result in immunosuppression (> 10 mg/day prednisone equivalents) for at least 2 weeks prior to study drug administration.
- Ocular melanoma
- Subjects with active, known or suspected autoimmune disease. Subjects with vitiligo, type I diabetes mellitus, residual hypothyroidism due to autoimmune condition only requiring hormone replacement, psoriasis not requiring systemic treatment, or conditions not expected to recur in the absence of an external trigger are permitted to enroll.

Subjects must also meet the study criteria including exclusion for medical history, positive hepatitis B/C, HIV and pregnancy tests, and the laboratory criteria described in [Section 3.3](#).

Study Drug: includes both Investigational [Medicinal] Products (IP/IMP) and Non-investigational [Medicinal] Products (Non-IP/Non-IMP) as listed:

Study Drug for CA209511		
Medication	Potency	IP
Nivolumab BMS-936558-01 Solution for Injection	100 mg (10 mg/mL)	10 mL per vial
Ipilimumab	200 mg (5 mg/mL)	40 mL per vial

Study Assessments:

Adverse events will be collected to determine the incidence of drug-related adverse events between the two cohorts.

Subjects will be observed for tumor response (ORR and PFS).

Subjects will be assessed by computed tomography (CT) or magnetic resonance imaging (MRI) beginning Week 12 (± 1 week) from randomization and continuing every 8 weeks (± 1 week) for the first 12 months and then every 12 weeks (± 2 weeks) until disease progression.

Subjects will be followed for Overall survival (OS) after disease progression or after drug-discontinuation.

Patient reported outcomes will be collected using the EQ-5D and EORTC QLQ-30

Statistical Considerations:

Sample Size: Approximately 346 subjects will be randomized to the 2 treatment arms in a 1:1 ratio in order to target 340 treated subjects (170 per arm). Given a two-sided alpha of 0.05, this number of treated subjects provides 80%

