3.1.2 Treatment Phase

- Begins with the randomization call to the IRT.
- Subject will be randomized to:
 - Arm A (N3I1): nivolumab 3 mg/kg + ipilimumab 1 mg/kg administered every 3 weeks for 4 doses or
 - Arm B (N1I3): nivolumab 1 mg/kg + ipilimumab 3 mg/kg ipilimumab are administered every 3 weeks for 4 doses.
- After combination therapy, all subjects will receive a flat dose 480 mg nivolumab IV every 4 weeks, beginning 6 weeks after the last combination dose, until progression or unacceptable toxicity.
- Treatment with Nivolumab will be limited to 2 years maximum duration.
- A negative pregnancy test should be documented within 24 hours prior to start of each dose of investigational product.
- Within 3 days from randomization, the subject must receive the dose of study medication.
- On study laboratory assessments should be drawn within 72 hours prior to dosing
- PK samples and immunogenicity samples will be collected according to the schedule in [Table 5.1-2](#) and [Table 5.1-3](#)
- Adverse event assessments should be documented at each clinic visit.
- Quality of Life will be assessed using European Organisation for Research and Treatment of Cancer Quality Of Life Questionnaire-core 30 (EORTC QLQ-C30) and European Quality of Life-5 Dimensions (EQ-5D) questionnaires, to be completed after randomization, prior to the first dose of study therapy and every 6 weeks for the first 6 months, and every 4 weeks until approximately week 40, according to the schedule in [Table 5.1-2](#).
- Study drug dose may be delayed for toxicity. See [Section 4.4.1](#).
- Treated subjects will be evaluated for response according to the RECIST 1.1 guidelines beginning 12 weeks (± 1 week) after randomization and continuing every 8 weeks (± 1 week) for the first 12 months, and then every 12 weeks (± 2 week) until disease progression or treatment discontinuation, whichever occurs later.
- This phase ends when the subject is discontinued from study therapy. For a complete list of reasons for treatment discontinuation, see [Section 3.5](#).

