5.4 Efficacy Assessments

Study evaluations will take place in accordance with the flow charts in [Section 5.1](#). Baseline assessments should be performed within 28 days prior to randomization utilizing CT or MRI. In addition to chest, abdomen, pelvis, and brain, all known sites of disease should be assessed at baseline. Subsequent assessments should include chest, abdomen, and pelvis, and all known sites of disease and should use the same imaging method as was used at baseline. Subjects will be evaluated for tumor response beginning 12 weeks (\pm 1 week) from randomization and continuing every 8 weeks (\pm 1 week) for the first 12 months and every 12 weeks (\pm 1 week) thereafter, until disease progression is documented or treatment is discontinued (whichever occurs later). Tumor assessments for ongoing study treatment decisions will be completed by the investigator using RECIST (Response Evaluation Criteria in Solid Tumors) 1.1 criteria.

Radiographic images will be collected and sent to a centralized imaging core laboratory for storage and potential future central reading.

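### Table 5.1-3, the synopsis and Section 8.3.2 end the 12-weekly scans at progression, but Sections 3.1.2 and 5.4 continue them while a patient is dosed beyond progression

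*Protocol*

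**What the plan says.** The protocol gives two end points for the 12-weekly tumor assessments.

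*Stop at progression:*
- Table 5.1-3 (on-study, Part 2), year-2 line: "From the second year from randomization, tumor assessments should occur every 12 wks (\pm 2 wk) until disease progression". The year-1 line just above it ("Subsequent tumor assessments should occur every 8 weeks") carries no stop at progression.
- Synopsis, Study Assessments: "every 12 weeks (± 2 weeks) until disease progression".
- Section 8.3.2, in the ORR paragraph, restates the schedule with the same end point.

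*Stop at the later of progression and end of treatment:*
- Section 3.1.2: "until disease progression or treatment discontinuation, whichever occurs later".
- Section 5.4: "until disease progression is documented or treatment is discontinued (whichever occurs later"). The same section gives a purpose: "Tumor assessments for ongoing study treatment decisions will be completed by the investigator using RECIST".

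Section 4.4.5 makes the difference matter. It lets a patient continue dosing after initial RECIST progression, within the 2-year maximum. It asks for one early scan: "A radiographic assessment/scan should be performed within 6 weeks of initial investigator-assessed progression". After that, a patient judged to be still benefiting should "continue to receive monitoring according to the Time and Events Schedule" in Section 5. Treatment must stop permanently at further progression, defined as a further 10% rise in tumor burden with at least 5 mm absolute increase from initial progression.

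**The concern.** For a patient who stops dosing at progression, the two rules give the same scans. They part only for a patient dosed beyond progression. That patient is subject to a mandatory stop that depends on lesion measurements.

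Section 4.4.5 sends the site to Section 5 for monitoring, and Section 5 holds both rules: Table 5.1-3 ends the year-2 scans at progression, and Section 5.4 does not. A site working from the table would do the scan within 6 weeks of progression. After that it would find no routine year-2 body imaging, only the roughly 12-weekly brain MRI for patients with a history of brain metastasis. Table 5.1-4 does not fill the gap, because its scans are limited to patients without progression on study therapy.

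What is at stake is patient management and safety: continued nivolumab in someone who already meets the measured stopping rule, with no scheduled scan to show it.

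**Working it through.** The plan gives no figure to reproduce, so the check lays the scan and dosing calendars side by side.

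**Inputs**
- Scans (Section 3.1.2, Table 5.1-3): Week 12, then every 8 weeks to 12 months, then every 12 weeks, giving Weeks 12, 20, 28, 36, 44, 52, 64, 76, 88, 100.
- Doses (Sections 4.3.1, 4.3.2, 4.5): combination at Weeks 0, 3, 6, 9. Part 2 starts at Week 9 + 6 = 15, then every 4 weeks to Week 103.
- Extra scan (Section 4.4.5): by 6 weeks after initial progression (PD).
- Assumed: first dose at Week 0, no delays, dosing to Week 104.

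**Formulas**
- Last required body scan under the table = later of Week 52 and PD + 6.
- Doses at risk = Part 2 doses after that scan, through Week 103.
- Weeks without a body scan = 104 minus the week of that scan.
- Comparator under Sections 3.1.2 and 5.4: 3 doses in 12 weeks between routine scans (for example Weeks 67, 71, 75 between scans at 64 and 76).

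| Initial PD | Last required body scan (table) | Doses after it | Excess over 3 | Weeks without body scan | Routine year-2 scans dropped |
|---|---|---|---|---|---|
| by Week 44 | 52 | 13 (Weeks 55 to 103) | 10 | 104 − 52 = 52 | 4 |
| Week 52 | 58 | 12 (Weeks 59 to 103) | 9 | 104 − 58 = 46 | 4 |
| Week 64 | 70 | 9 (Weeks 71 to 103) | 6 | 104 − 70 = 34 | 3 |
| Week 76 | 82 | 6 (Weeks 83 to 103) | 3 | 104 − 82 = 22 | 2 |
| Week 88 | 94 | 3 (Weeks 95, 99, 103) | 0 | 104 − 94 = 10 | 1 |

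For PD at Week 88 the longest run is no greater than the nominal 3, but the Week 100 scan is still dropped.

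**Sensitivity**
- Scan windows, comparator: with ±2 weeks, scans at Weeks 62 and 78 bracket doses at 63, 67, 71 and 75, so the fuller rule can itself give a run of 4. The excess over 4 is 9, 8, 5, 2 and 0.
- Scan windows, table: moving scans within their windows and taking the post-PD scan 2 to 6 weeks after PD gives runs of 13, 11–13, 8–10, 5–7 and 2–4.
- Start of Part 2: the protocol also labels it Week 16 (Table 5.5.1-1 footnote) and Week 18 (Section 5.3). Week 16 leaves the counts unchanged. Week 18 gives 13, 11, 8, 5 and 2.

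**Effect on the analyses**
- SAP 4.2.1 and 4.2.2 take BOR up to, and PFS at, first RECIST progression. Later scans enter neither.
- The primary endpoint definition uses no scan. Section 3.1.3 plans the primary analysis about 13 months after randomization starts: 13 × 52.18/12 = Week 56.5 for the first patient. The first disputed scan is at Week 64, or Week 62 at the earliest.

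**The case against.** The strongest case against is that the protocol already states the right rule twice. Section 5.4 is the dedicated efficacy-assessment section and lies within the part of the protocol to which Section 4.4.5 refers. On this view a table note and a summary were not harmonised, and no scan is missing from the plan. The protocol also uses the same shorthand for dosing: the synopsis, Section 3.1.2, Section 4.3.2 and the footnote to Table 4.5-2 all end treatment at progression, with Section 4.4.5 as the exception. A site that took the shorthand literally would stop dosing too, and no gap would arise.

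Other safeguards also remain. Continued dosing requires clinical benefit, tolerance and stable performance status (4.4.5). Weight and ECOG are checked at each Part 2 dose and LDH at alternate doses (Table 5.1-3). Treatment must stop for substantial clinical risk (4.4.4). Extra assessments are allowed as clinically necessary (5.3), and the further-progression rule itself prompts a site to image.

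Much of this stands. The intended rule is clear, the harm needs a site to follow the table against two explicit sections, and the dose counts are worst cases. Three things do not go away. Nothing in the documents says that the text overrides the table. Section 4.4.5 expressly lifts the dosing limit but, for scans, adds only the one early scan and a reference to Section 5. And clinical checks do not measure 10% and 5 mm, while unscheduled imaging is permitted but not required.

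A reader might infer more than this:
- *That the plan deliberately leaves patients dosed beyond progression unscanned.* Sections 3.1.2 and 5.4 say the opposite.
- *That ORR or PFS is biased.* Both rest on first RECIST progression.
- *That year-1 scans also lapse under the table.* The table attaches the stop only to its year-2 line.

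**Conclusion.** The inconsistency is real and worth correcting on patient-safety grounds. Three places end the 12-weekly scans at progression, two continue them to the later of progression and treatment discontinuation, and a mandatory stopping rule depends on which one a site follows.

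The size is a conditional worst case: up to 13 doses over 52 weeks without a required body scan, falling to 3 doses over 10 weeks for progression at Week 88. It assumes that the site follows the table, that dosing runs undelayed to Week 104 with lasting clinical benefit, and that the scans that are done show no further progression. The documents give no basis for the number of such patients. Section 4.4.5 itself expects benefit after initial progression in only a minority. Confidence is high in the textual conflict and lower in how often it would change care. The trial's conclusions are not affected.

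**What to change.** In Table 5.1-3 (year-2 line), the synopsis schedule and Section 8.3.2, replace the end point at disease progression with the Section 3.1.2 wording: "until disease progression or treatment discontinuation, whichever occurs later". Section 8.3.2 needs the edit as well, or the contradiction stays in the statistical section.

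As a minor and separate edit, change the 12-weekly window in Section 5.4 from ±1 week to ±2 weeks, to match Table 5.1-3, the synopsis and Section 3.1.2.

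The cost is three clauses and one number. No scan is added beyond those that Sections 3.1.2 and 5.4 already require, and no endpoint definition or analysis changes.
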